Heart transplant patients with CAV who primary transplant followup care at the University of Nebraska will serve as the study cohort. Given the complexity of heart transplant patients, care is highly-protocolized and organized according to graft age. Care is most intensive in the first year following transplant wherein patients are initially evaluated on a weekly basis for the first month with reduced frequency (biweekly \rightarrow monthly \rightarrow quarterly) based on clinical progress over the first year. During year 2 post transplant, stable post-transplant patients are typically seen quarterly and this extends to biannual evaluations during year 3. After 3 years, stable post-transplant patients can often be seen on an annual basis. Thorough evaluations are completed annually including comprehensive labwork (complete blood count, complete metabolic panel, fasting lipid panel, thyroid function tests, hemoglobin A1c, creatinine kinase, urine protein analysis), assessment for donor specific antibodies, and imaging/testing. Imaging/testing includes an annual echocardiogram and chest x-ray as well as other imaging (DEXA scan, carotid and abdominal ultrasounds) at frequencies determined by comorbidities. Immunosuppression is maintained with calcineurin inhibitors (primarily tacrolimus) and DNA synthesis inhibitors (mycophenolate mofetil, mycophenolic acid or azathioprine). Patients are switched to mTOR inhibitors (primarily sirolimus) if significant renal dysfunction develops or CAV is diagnosed. High dose steroids are started at the time of transplant and typically weaned off during the first year. Calcineurin inhibitors and mTOR inhibitors are dosed according to trough serum levels, and thus monitored at least every three months indefinitely.

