Assess the effect of evolocumab on CAV progression. All patients enrolled will have CAV documented by cardiac angiography. Standard post-transplant care includes annual angiograms in patients diagnosed with CAV to monitor for disease progression. CAV progression will be defined as an increase of one CAV grade (CAV-1 \rightarrow CAV-2 or CAV-2 \rightarrow CAV-3). The number of patients with CAV progression of at least one grade while on evolocumab will be compared to historical controls for our transplant program. Percentage diameter stenosis for each vessel with visible CAV also will be determined by quantitative coronary angiography (QCA) using Philips Xcelera software package in a blinded fashion by an experience interventional cardiologist for patients angiograms completed one year prior to study entry, at study entry, and study conclusion. Angiographic change while on evolocumab therapy will be compared to the preceding year.

Assess the effect of evolocumab on immunosuppression regimens and graft rejection. Transplant patient are maintained on lifelong immunosuppression. These agents are prone to significant drug-drug interactions which can limit therapies. Serum levels of immunosuppression are monitored every three months per standard protocol. Measured serum levels at 3, 6, 9, and 12 months, as well as the number of dose adjustments while on evolocumab therapy while on evolocumab therapy will be compared to the preceding year. Statistical adjustment for confounding factors such as changes in renal function or other drugs known to alter immunosuppression levels (i.e. diltiazem, certain antimicrobial drugs) will be completed. In addition, the incidence of transplant rejection will be documented while on evolocumab therapy and compared to the prior year. Transplant rejection will be defined as symptoms requiring therapeutic intervention or endomyocardial biopsy findings of ≥grade 2 or positive C4d staining or new donor specific antibodies.

Measure the effect of evolocumab on serum lipids including HDL and triglycerides after 1 year of therapy. Fasting lipid profiles (total cholesterol, LDL, HDL and triglycerides) after 52 weeks of evolocumab therapy will be compared to baseline levels. Fasting lipid profiles are assessed annually as part of routine post-transplant care. The percentage change of LDL, HDL and triglyceride from baseline will be calculated after 1 year of evolocumab therapy.

Statistical analysis is detailed in Section 8 below.

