All suspected unexpected serious adverse reactions (SUSARs) related or possibly related to evolocumab and their follow-up reports will be reported to Amgen within 24 hours of submission to the regulatory agency or IRB. Amgen will be informed of any pregnancy occurring and/or existing during exposure to the investigational medicinal

product and pregnancies occurring in the partner of a patient participating in the study and potential infant exposure within ten (10) calendar days of sponsor awareness.

Section 8. Statistical Analysis Plan

Statistical analysis will be completed with the direct assistance of faculty from the University of Nebraska biostatistics department. Sample size (n=40) is chosen based on the size of the heart transplant clinic (the number of heart transplant patients with CAV expected to be eligible for study participation).

The primary outcome is percentage change from the baseline in LDL levels after 12 weeks of evolocumab therapy. Prior trials have demonstrated that evolocumab lowers LDL cholesterol at week 12 by greater than 50% from baseline[2, 3]. The sample size of n=40 is expected to yield greater than 99% power to detect 50% reduction of LDL cholesterol from baseline after 12 weeks of evolocumab therapy at a significance level of 0.05 using a two-sided Wilcoxon signed-rank test, assuming the estimated standard deviation of reduction of 0.17.

Descriptive statistics will be presented as frequencies and percentages for categorical variables, and mean ± standard deviation, or median with range for continuous variables, unless otherwise indicated. Paired t-tests or Nonparametric Wilcoxon signed-rank tests will be completed where appropriate to compare the primary endpoint before and after 12 weeks of evolocumab therapy, and compare continuous secondary endpoints after 1 year of evolocumab therapy to baseline. A linear mixed model analysis will be conducted to analyze immunosuppression serum levels measured at baseline, 3 months, 6 months, 9 months, and 1 year of evolocumab therapy. The binary secondary endpoint of CAV progression will be assessed after 1 year of evolocumab therapy using McNemar tests. Safety data will be reported with frequencies and percentages. All tests will be two-tailed. A p-value <0.05 will be considered significant. Analysis will be performed using SAS version 9.4 (SAS Institute, Cary, NC).

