Given the limited statistical power due to the small cohort, conclusions from secondary endpoints are expected to by primarily hypothesis-generating with data providing support for potential future studies.

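### Section 8 models immunosuppressant levels from one baseline with no dose term, although Secondary endpoints promises a preceding-year comparison and the drugs are dosed to trough

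*Combined protocol and SAP*

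**What the plan says.** All places are in the combined protocol and SAP.

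- Secondary endpoints gives the reason for this endpoint: "These agents are prone to significant drug-drug interactions which can limit therapies". Levels at months 3, 6, 9 and 12 are to be set against the year before treatment, and so is the dose-adjustment count: "number of dose adjustments while on evolocumab therapy while on evolocumab therapy will be compared to the preceding year". It also promises "Statistical adjustment for confounding factors such as changes in renal function or other drugs known to alter immunosuppression levels", and refers the reader to Section 8 for the analysis.
- Section 8 provides one model: "A linear mixed model analysis will be conducted to analyze immunosuppression serum levels measured at baseline, 3 months", then months 6, 9 and 12.
- Standard post-transplant care states the dosing rule: "Calcineurin inhibitors and mTOR inhibitors are dosed according to trough serum levels". On frequency, Secondary endpoints says: "Serum levels of immunosuppression are monitored every three months per standard protocol".
- Standard post-transplant care also says: "Patients are switched to mTOR inhibitors (primarily sirolimus) if significant renal dysfunction develops or CAV is diagnosed". CAV is an entry criterion, so mixed agents and recent switches can be foreseen.
- The end of Section 8 limits the claims: "conclusions from secondary endpoints are expected to by primarily hypothesis-generating".

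**The concern.** There are two separate problems.

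First, the endpoint text and the analysis text do not match. The comparator differs (preceding year against one baseline), the promised adjustment does not appear in the model, no contrast is named, and the dose-adjustment count has no method. An analyst following Section 8 would not deliver what Secondary endpoints describes, and would lose precision.

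Second, the outcome being modelled drives the dose. If evolocumab changed exposure at a given dose, titration would return the level towards target and part of the change would move into the dose. A flat raw level may then mean either no interaction or one that titration has corrected. The count helps only partly, because it has no direction: more increases can be offset by fewer decreases.

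At stake is a secondary safety question, and the future studies that these data are meant to support. The primary LDL endpoint is not affected.

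**Working it through.** **1. The plan's own figure.** The documents give no power or precision for this endpoint. The only power statement, above 99% for LDL, reproduces: 0.50/0.17 × √40 = 18.6 standard errors, power 1.00. It has no bearing here.

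**2. The two texts side by side.**

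| Item | Secondary endpoints | Section 8 |
|---|---|---|
| Comparator | Preceding year | One baseline value |
| Covariates | Renal function, interacting drugs (open list) | None named |
| Contrast | On treatment v preceding year | None named |
| Dose-adjustment count | Compared with preceding year | No method |
| Dose in the level model | Not named | Not named |
| Different or switched agents | Not addressed | Not addressed |

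**3. Cost of one baseline.** For dose-normalised log levels with independent residuals, the variance of the on-treatment mean (four values) minus the comparator is proportional to 1/4 + 1 with one baseline and to 1/4 + 1/4 with four preceding-year values. The ratio of standard errors is √(1.25/0.50) = 1.58. For a true -20% and n = 40, with standard error SD × √(1.25/40) or SD × √(0.50/40), the 95% intervals are:

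- SD 0.35: about -29% to -9% with one baseline, -26% to -13% with four values.
- SD 0.25: about -27% to -13% with one baseline, -24% to -15% with four values.

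**4. Why raw levels attenuate.** Write log level = log dose + patient effect + shift + error. If titration has offset a fraction g of the shift, the raw level shows (1 - g) × log 0.80. This is -20% at g = 0, -11% at g = 0.5 (0.80^0.5 = 0.89) and 0% at g = 1. At g = 1 the dose has risen by 1/0.80 - 1 = 25%. Level divided by dose shows -20% throughout.

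**5. Illustration.** These inputs are assumptions, not document figures: 20% fall at fixed dose, within-patient log SD 0.25-0.35, 40 patients on one agent, 50-100% correction when the log deviation exceeds 0.2. Checks are quarterly, as in the protocol. There were 4,000 simulated trials per setting, with tests on within-patient differences. Ranges span the SDs, the degree of correction, and two dosing histories: dose titrated at every check before entry, or unchanged until after the month-3 level.

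Mean raw level is -20% at month 3, -11% to 0% at month 6 and -3.5% to 0% at month 12. The month-12 dose is 21-25% higher.

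| Power, true -20% | Raw | Dose-normalised |
|---|---|---|
| On-treatment mean v one baseline | about 0.10-0.75 | 0.94 or more |
| On-treatment mean v four preceding-year values | about 0.36-0.99 | about 1.00 |
| Month 3 v one baseline | about 0.36-0.98 | 0.78-0.98 |
| Month 3 v preceding year | about 0.69-1.00 | not tabulated |
| Joint test over Section 8's five visits | 0.40-0.97 | 0.77-0.99 |

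**6. The undirected count.** Where doses are already titrated before entry, its power is 0.05-0.11 at trigger 0.2 and 0.05-0.29 at trigger 0.4. At trigger 0.2 the rule makes 1.95-2.74 changes per patient over four pre-treatment checks, so about half to two thirds of checks change the dose with no drug effect. No passage supports that rate. The count's power therefore reflects the assumed rule and is not evidence in itself.

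**The case against.** The endpoint concerns immunosuppression regimens, not levels alone. Dose adjustments are already half of it, and the confounder list is open, so dose could be added. Raw levels answer a legitimate question: do levels stay on target under usual titration? Secondary results are declared hypothesis-generating. Carrying out the preceding-year comparison as written, with no dose term, recovers much of the lost power. Dose-normalising brings its own assumption of approximate dose-proportionality and needs same-agent values, which a recent switch removes.

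Most of this stands. It is why the mismatch between the two texts comes first and why the dose-normalised model is proposed as supportive. It does not remove the attenuation: with full correction, raw power for the on-treatment mean stays well short of the dose-normalised figure even against four preceding-year values. Nor does an open covariate list prespecify a dose analysis.

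A reader might infer three stronger things that the documents do not support:

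- *The model cannot see an interaction.* It is weakened, not blind. The month-3 level may precede any correction, and several raw contrasts keep useful power in part of the range.
- *The plan will declare no interaction from a null level.* No section says so.
- *The plan ignores dose.* It counts dose adjustments. What it lacks is their direction and a method.

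**Conclusion.** The mismatch between Secondary endpoints and Section 8 is a matter of text and needs no assumption. Its cost is a standard error 1.58 times larger for dose-normalised levels, given independent residuals.

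The attenuation of raw levels follows from the trough-dosing statement, which covers calcineurin and mTOR inhibitors and not the DNA synthesis inhibitors. How large it is depends on the assumed effect, SDs and titration rule, and the wide power ranges show how much. What holds without those assumptions is that a null raw-level result, taken alone, does not show absence of an interaction, and that an undirected count is only a partial safeguard.

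The consequence is modest. The change is still worth making because it is cheap.

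**What to change.** In Section 8:

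1. Include the preceding-year quarterly levels, with a period contrast (before v on treatment) and the covariates promised in Secondary endpoints. Report the month-3 contrast as well.
2. Add a supportive mixed model of log dose-normalised trough (level divided by the total daily dose in effect when it was drawn), fitted within agent and using same-agent values only.
3. Keep raw levels as a description of levels under usual titration. Report dose increases and decreases separately against the preceding year.
4. Give ratios with 95% confidence intervals, and state that a null raw-level result is not read as absence of an interaction.

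**Cost.** SAP wording, and recording the dose with each level. Counting adjustments already requires the doses to be read, and preceding-year data are already called for.

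**Downsides.** Fewer patients are usable per agent, especially after a switch to an mTOR inhibitor at CAV diagnosis; a patient with no pre-treatment value on the current agent gives no within-patient contrast. Under the same assumptions, dose-normalised power with 20 patients is 0.96 or more against four preceding-year values and 0.68-0.93 against one baseline. With 10 patients it is 0.72-0.94 and 0.37-0.61. Approximate dose-proportionality is also assumed: with a dose exponent of 0.8 a true -20% is estimated as -22% to -23%, and with 1.2 as about -18%, with no bias when the true effect is zero.
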